## 2. Study Conduct

The study will be conducted according to the protocol, Good Clinical Practice (as outlined in the ICH Guidelines and Code of Federal Regulations), and the Declaration of Helsinki. Written informed consent for the study must be obtained from all subjects prior to protocol specific procedures being performed. Subjects must be informed of their right to withdraw from the study at any time.

## 3. Study Oversight

The principal investigator has primary oversight responsibility for this trial. The PI will meet with the study coordinator, as well as any other necessary members of the research team as needed. The meetings will include reviews of safety data, protocol deviations, adverse events, subject compliance, test article accountability and inventory, logs for screening, enrollment, and subject withdrawal, as well as any other pertinent issues identified by the PI, study coordinator, or other research team member.

#### 4. Data Safety Monitoring Board

Working under the direct guidance of the FDA, a qualified data safety monitoring board (DSMB) has been established. Written procedures for monitoring of the clinical trial to assure the quality of the study and to assure that each person involved in the monitoring process carries out their duties will be set to comply with FDA regulations. These monitoring procedures will be included in a Manual of Operations for the study.

#### 5. Interim Analyses for Safety and Efficacy

Interim analyses of safety data will be performed periodically throughout the project. While the safety of subjects will be the primary concern of the data safety monitoring board (DSMB), it is difficult to formulate precise stopping guidelines that would cover all of the possible situations that might arise. Adverse events, particularly serious adverse events such as deaths and hospitalizations, will need to be carefully considered by the DSMB in terms of treatment group imbalances. It is helpful to emphasize that our previous double-blind, randomized crossover trial of 20 DM1 patients treated with 150 mg three times daily of mexiletine for 7 weeks was completed without any significant adverse events; and, that a subsequent second double-blind, randomized crossover trial of 20 DM1 patients treated with 200 mg three times daily of mexiletine for 7 weeks was also completed without any significant adverse events. We do not anticipate encountering any expected side effect that based upon our advanced knowledge of mexiletine will constitute a reason to stop the study or specifically stop a given patient's participation. Severe confounding medical illness or severe trauma are reasons noted previously in this application for discontinuing patient participation. We perform serial laboratory studies throughout the course of the treatment trial. If the DSMB observes trends in all patients that suggest that a given value(s) is rising or falling 2-3 fold outside the normal range and is not known to occur in the usual clinical course of DM1, this finding will prompt a discussion of the need to stop the study. The same actions will occur if a serious medical illness develops in a significant portion of the DM1 patients receiving mexiletine which is not typically observed in the usual clinical course of a DM1 patient.

In addition, we will perform an interim analysis of the primary outcome variable after 50% of the trial participants (20 participants) have completed 6 months of follow-up. We will use an O'Brien-Fleming stopping boundary whereby the interim analysis will be performed using a significance level of 0.003 and the final analysis will be performed

using a significance level of 0.049 (two-tailed). This will ensure that the overall probability of a Type I error is controlled at 0.05.

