## D. RESEARCH DESIGN AND METHODS:

### TRIAL DESIGN:

#### SCHEMATIC SUMMARY OF MEXILETINE TREATMENT IN DM1

This FDA Orphan Product Development Project proposes a double-blind, randomized, placebo-controlled, six month clinical trial of the efficacy and safety of mexiletine (150 mg three times daily) for the treatment of moderately affected ambulatory patients with DM1. Twenty patients will be randomized to receive treatment while another 20 patients will receive placebo. Patients will be randomized in a 1:1 ratio to receive either mexiletine (150 mg three times daily) or placebo. The primary outcome measure will be the assessment of ambulation by six minute walk time. Secondary outcome measures will include: a) grip myotonia as determined by relaxation time following maximum voluntary isometric contraction of the finger flexor muscles; b) muscle strength; c) change in lean muscle mass; d) pain measurement using the Brief Pain Inventory and a

modified Chronic Pain Scale; e) Gastrointestinal function measured by two gastrointestinal questionnaires; f) The ability to swallow as measured by a timed swallowing test with water; g) physical function as measured by the time to rise from a chair, Purdue Peg Board Score, time to walk 30 feet, six minute walk, and SF-36; and, h) pulmonary function (measured by serial determinations of forced vital capacity); i) change in Holter monitor data from baseline; and j) patient relevance as measured by a novel disease-specific health-related quality-of-life instrument designed specifically as an clinical outcome measure for the DM1 population.

During the trial of treatment with mexiletine, all patients will receive careful safety monitoring, including serial EKGs, laboratory testing, three in-person evaluations on the University of Rochester NIH funded Clinical Translational Sciences Institute sponsored Clinical Research Center, and phone calls to assess for any side effects or problems with the study medications, to encourage adherence to the treatment regimen, and to grade musculoskeletal pain. Below is a more detailed description of the study design and the outcome measures.

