### **Statistical Analyses:**

The primary outcome variable in this clinical trial will be the change from baseline to Month 6 in the mean distance walked during the six minute walk test. Using historical six minute walk test data in the DM1 population, we will have 80% power to detect a group mean change of 183 feet in distance walked over six minutes. The primary statistical analysis will involve fitting a repeated measures analysis of covariance model with treatment group as the factor of interest and the baseline value of the outcome variable as a covariate. The model will also include terms for month (categorical) and the interaction between treatment group and month. An unstructured covariance pattern will be used for model fitting. This model will be used to determine a 95% confidence interval for the adjusted mexiletine – placebo difference in mean response (treatment effect) at Month 6. Confidence intervals for treatment effects at Month 3, as well as averaged over Months 3 and 6, can also be obtained using this model; these will be considered to be secondary analyses.

If clinically important differences are found between the groups at baseline, particularly with regard to important variables such as age, gender, and years since symptom onset, the primary analyses will be repeated after statistically adjusting for these differences. These sensitivity analyses will be considered to be secondary, however.

The underlying assumptions of the analysis of covariance model will be thoroughly checked (e.g., normality, linearity), including analyses of residuals. Remedial measures (e.g., transformations, use of nonparametric methods) will be taken if serious violations of these assumptions are detected.

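### The plan allows an efficacy stop at about 10 v 10 completers but gives no rule for estimating the effect after one; at the planning values the plain estimate would then average about 64% too high

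*Combined protocol and SAP*

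**What the plan says.** Section E, Data and Safety Monitoring Plan, item 5 (Interim Analyses for Safety and Efficacy) states: "we will perform an interim analysis of the primary outcome variable after 50% of the trial participants (20 participants") have completed six months. It continues: "We will use an O'Brien-Fleming stopping boundary whereby the interim analysis will be performed using a significance level of 0.003", with 0.049 two-tailed at the end. The stated purpose is error control: "This will ensure that the overall probability of a Type I error is controlled at 0.05". Allocation is equal (Schematic Summary: "Patients will be randomized in a 1:1 ratio"), so the look falls at about 10 v 10.

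The only estimator is in section D, Statistical Analyses, for the repeated measures ANCOVA: "This model will be used to determine a 95% confidence interval for the adjusted" group difference at Month 6. Nothing in the document gives a repeated or stage-wise interval, a stopping-adjusted estimate, or a reporting rule for an early stop.

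Two other places bear on this. Statistical Analyses and the section on withdrawal, discontinuation and dosage reduction commit the primary analysis to intention to treat, covering every randomised patient and all data collected. Neither says what happens to patients still short of Month 6 when a stop is called.

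**The concern.** A boundary at 0.003 with 20 patients is crossed mainly when the observed difference is large by chance, the observed SD is small by chance, or both. An ordinary estimate and interval taken at that moment ignore this selection. The estimate is then too high on average and the interval is both off-centre and too narrow, unless the true effect is large.

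The document says the results may lead to approval of mexiletine as an orphan therapy for DM1. An early stop is the case in which the walk effect would be quoted most, from the fewest patients. The reporting rule has to be written before unblinded data exist, because a rule chosen afterwards can be questioned.

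**Working it through.** **Inputs.** Detectable difference 183 ft, SD 190 ft, 18 evaluable per group raised to 20 for 10% withdrawal (Sample Size Considerations). Look at 20 completers, levels 0.003 and 0.049 (item 5). 1:1 allocation (Schematic Summary).

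**1. The plan's own figures reproduce.** Noncentrality = 183 / (190 × √(2/18)) = 183 / 63.33 = 2.889. With 34 df, power is 80.2% at two-sided 0.05 (79.9% at 0.049). 18 / 0.90 = 20. Two looks at information 0.5 and 1 with levels 0.003 and 0.049 (z = 2.968 and 1.969, correlation √0.5) give an overall alpha of 0.04998.

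**2. The boundary in feet.** SE at 10 v 10 = 190 × √(2/10) = 84.97 ft. The critical t at two-sided 0.003 on 18 df is 3.428. 3.428 × 84.97 = 291 ft, or 1.59 × 183. That threshold applies only if the observed SD is 190 ft. Among crossing trials the observed SD averages about 164 ft, and 3.428 × 164 × √0.2 = 251 ft. About 45% of crossing trials have a difference below 291 ft.

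**3. Plain estimate and 95% interval, given a crossing.** Two-arm normal simulation, two-sample t-test on 18 df, at least 1 million trials per setting, 20 completers only:

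| True effect, SD (ft) | Trials crossing | Mean estimate / truth | 95% interval covers |
|---|---|---|---|
| 183, 190 | 14.3% | 301 / 183 = 1.64 | 82% |
| 91.5, 190 | 2.2% | 269 / 91.5 = 2.94 | 11% |
| 300, 190 | 55% | 353 / 300 = 1.18 | 95% |
| 183, 150 | 29% | 253 / 183 = 1.38 | 91% |
| 183, 230 | 8% | 350 / 183 = 1.91 | 70% |

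Using 17 df for the baseline covariate leaves the first row at 1.64 and 82%.

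**4. Check by formula.** In the normal approximation the threshold is 2.968 × 84.97 = 252 ft, so a = (252 − 183) / 84.97 = 0.814. Conditional mean = 183 + 84.97 × φ(a) / (1 − Φ(a)) = 183 + 84.97 × 1.378 = 300 ft, again 1.64. Conditional coverage = (Φ(1.96) − Φ(0.814)) / (1 − Φ(0.814)) = 88%. The t calculation is lower, at 82%, because crossing also selects small observed SDs.

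**5. Over all trials, stopped or not (183 ft, SD 190).** Mean estimate 191.4 ft, so (191.4 − 183) / 183 = 4.6% bias. Coverage is about 94%.

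**6. Adding patients already randomised.** With steady accrual of r per month and no losses, 20 + 6r are randomised at the look: 32 at r = 2, all 40 from about r = 3.4. If all of them reach Month 6 on their assigned arm, then given a crossing at 183 ft and SD 190:

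| Patients | Mean estimate (ft) | Plain 95% interval covers |
|---|---|---|
| 32 | 257 (+40%) | 85% |
| 40 | 242 (+32%) | 87% |

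More than 99% of these results keep p < 0.05 at the planned effect; at half of it, 93% (32 patients) and 91% (40).

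**7. A 99.7% interval at the stop**, matching the 0.003 level, covers about 99% given a crossing at 183 ft, and about 94% at a true 100 ft. It leaves the point estimate unchanged.

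**The case against.** The strongest reply is that the design does what it promises. Type I error is held. At the planning values a crossing is a one-in-seven event, and over all trials the estimate is nearly unbiased. Reporting the ordinary estimate with the early stop disclosed is common practice. The 183 ft is a detectable difference, not a claim about the truth, and at a true 300 ft the overstatement is modest. That the plain estimate would be reported is inferred from the absence of any other. Month 3 data from patients in follow-up would enter the likelihood model and were not modelled here. Monitoring procedures are also deferred to a Manual of Operations that is not among the documents.

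All of this limits the size of the point. It does not supply the missing rule.

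Four stronger readings are tempting, and the documents do not support them:

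- A reader might infer that a crossing needs at least 291 ft, so that any crossing result is too large by construction. The boundary is a t statistic and nearly half of crossings fall below 291 ft. The bias is an average that depends on the true effect.
- A reader might infer that patients short of Month 6 are left out of the reported effect. The plan does not say so, and its stated analysis set is everyone randomised.
- A reader might infer that safety would rest on about 10 treated patients. Adverse events are recorded for every patient from consent (Reporting of adverse events), so all those randomised by the look contribute.
- A reader might infer an error-rate fault in the 0.003/0.049 pair. The calculation shows none.

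**Conclusion.** The point stands as a gap in estimation and reporting. The plan prespecifies a stop for efficacy but not how to estimate the effect after it. Using its only stated method on the 20 completers overstates the walk effect by 64% on average, with about 82% coverage (88% by normal approximation). These figures are conditional on crossing, on a true effect of 183 ft and on an SD of 190 ft. The problem grows quickly as the true effect falls below 183 ft or the SD rises, and it is mild for large effects. It is worth correcting because the remedy is cheap and must be fixed in advance. It does not call the boundary, the significance levels or the sample size into question.

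**What to change.** Keep the look and the 0.003/0.049 levels. Add to item 5 that, if the boundary is crossed:

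- **(a)** The interim effect is reported with the 99.7% repeated interval and a named stopping-adjusted estimate, with its formula. The choice matters. The stage-wise median-unbiased estimate is a familiar candidate, but for a stop at the first look its ordering uses only the interim result, so it is in effect the plain estimate. An estimate conditional on crossing addresses the bias shown here. In the normal approximation above, the conditional mean at a true 183 ft is 300 ft, so matching on that mean would take an observed 300 ft back to 183 ft. It is more variable, and the plan should say so.
- **(b)** In line with the intention-to-treat commitments, Month 6 walk data from all patients already randomised are collected where available. The primary model is also reported on all of them, with an interval that allows for the stop, for example one computed conditionally on crossing.

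The text should say that (b) alone is not enough: with a plain 95% interval it still gives about 257 ft (32 patients) or 242 ft (40 patients) and 85 to 87% coverage. Those figures assume an accrual rate and that patients stay on their assigned arm to Month 6. What happens to treatment after a stop is for the sponsor and the DSMB.

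The cost is some added wording, a little extra analysis, a possible wait of up to six months for Month 6 data, and a wider interval around a smaller estimate.

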## 6. Independent Medical Monitor

The independent Medical Monitor (Dr. [REDACTED]) will be responsible for monitoring the conduct and progress of the study as well as evaluating clinical situations and communicating new safety information to the PI and the FDA. The independent Medical Monitor will review aggregate data (adverse events and safety labs) and ascertain whether adverse events are thought to be occurring more frequently than expected. If they are, they will be reported by memo to the PI and the DSMB. The independent Medical Monitor will review the SAE notification form to determine if the event is unexpected and associated with the use of study medication. The site may be called to provide further information, if necessary. The progress of each SAE will be followed by the independent Medical Monitor until resolution or until an appropriate endpoint is reached (resolution or determination of the event to be chronic and/or stabilized).

## 7. Adverse Event Monitoring

The PI will review data regarding adverse events and laboratory abnormalities in a blinded fashion. An independent medical monitor will receive and review reports of all adverse events. The independent DSMB can review unblinded data as necessary. In the rare event that an investigator needs immediate knowledge of the subject's treatment assignment for emergent care of the subject, individual treatment assignment envelopes generated by the Biostatistics Center will be available.

## 8. Data Management

The original Case Report Forms (CRFs) for each visit will be sent to the Neuromuscular Disease Data Center (NMD-CC), with a duplicate copy stored in the subject's research chart. All original and duplicate CRFs will be kept under double lock by the Data Manager at the NMD-CC. Completed CRFs will be entered into a SAS database on the Neurology file server. Access to study subject CRFs and Statistical Analysis Software (SAS) database will be limited to study personnel. For each CRF, custom data entry screens will be developed with error checking built in using SAS/FSP software by the Study Data Manager. SAS/FSP software provides convenient interactive capabilities for data entry, editing, and retrieval.

To minimize data entry errors Screen Control Language (SCL) will be developed to edit individual fields and perform cross-field validation. When SCL detects an invalid data value, entry is suspended. An appropriate error message is displayed, prompting the data entry clerk to resolve the discrepancy before entry can be completed. Batch SAS programs will also check for inconsistencies and incompleteness of data after initial entry. The Data Manager will develop edit check programs, and these programs will generate output that describes data discrepancies found in the database. All CRFs are

reviewed for clarity and completeness. In addition, all output generated by the edit check program will be reviewed by a Data Manager. Data discrepancies identified through edit check programs, manual review of CRFs, or clinical reviews will generate queries which will be e-mailed to the investigator/coordinator on a Data Clarification Form (DCF). The DCF will identify the subject, visit number, CRF number, and the data element flagged for review. The study coordinator will investigate the discrepancy. The DCF must be completed showing what corrections need to be made (or indicating why no changes are necessary) and signed by the site investigator or coordinator, then faxed back to the NMD-CC. Data entry staff at the NMD-CC will enter the response to the DCF into the database and the data manager will verify that they have been entered correctly. The original DCF will be filed by the study coordinator with the corresponding CRF source documents.

All DCFs should be returned to the NMD-C within two weeks after the DCF was sent to the investigator/coordinator. All completed CRFs should be sent to the NMD-CC with two weeks after each study visit. Any CRF or DCF that is not received within the two weeks will generate request to the coordinator with a copy to the investigator.

NMD-CC Data Manager will perform a final quality audit of a random sample of 5 patients at the end of the study. All CRFs from the random sample of patients will be 100% verified against the database. If the error rate is less than or equal to 0.1% (an accuracy rate of at least 99.9%) and the errors encountered are not significant, NMD-CC will correct the errors and finalize the database. If the error rate is greater than 0.1% or if the errors encountered are significant (i.e. an adverse event was not entered), a rework of these sections of the database will be performed, and these sections will be re-audited on another 5 patient random sample.

Upon completion of the study, the cleaned databases are locked and sent to the study biostatistician for final analysis.

## 9. Risk/Benefit Assessment

We believe that the relatively mild side effects and risks of treatment associated with mexiletine in patients with DM1 will be heavily outweighed by the likely improvement in their muscle function resulting from this treatment. If our results lead to a new approved indication for the use of mexiletine as an antemyotonia therapy, this finding will have a wide beneficial effect for all patients with DM1.

## **Inclusion of Women and Minorities**

Myotonic dystrophy (DM-1) has a prevalence rate of approximately 1 per 7,500. We anticipate that our study population will have no gender differences, but there may be a relative predominance of certain ethnic backgrounds. The prevalence rates of DM1 in major ethnic populations have not been established within the United States, but DM1 prevalence rates in Africa are much lower than those in Europe and the United States. The demographics of myotonic dystrophy in Monroe County are not known.

However, the latest demographics of Monroe County (White 80.8%, Black 14.7%, Hispanic 5.7%, Asian 2.8%, Native American 0.3%) indicate that our area contains

minority populations similar to the national distribution (<http://quickfacts.census.gov/qfd/index.html>; accessed on 2/2/2009). We have based our recruitment projections to reflect the demographics of Monroe County which closely parallel those of the general U.S. population. We will send information describing this study to the local and national offices of the Muscular Dystrophy Association as well as the NIH. It is our hope that this will increase the diversity of the patients enrolled in our clinical trial. Based on the above information, we expect the ethnic distribution of enrollment to be as indicated in the Table 3.

### **Targeted/Planned Enrollment**

**TABLE 3:**

#### **Targeted/Planned Enrollment Table**

**Study Title:** A Randomized, Placebo Controlled, Clinical Efficacy Trial of Mexiletine for Myotonic Dystrophy Type-1 (DM1).  
**Total Planned Enrollment:** 60 myotonic dystrophy patients

TARGETED/PLANNED ENROLLMENT: Number of Subjects			
Ethnic Category	Sex/Gender		
	Females	Males	Total
Hispanic or Latino	2	2	4
Not Hispanic or Latino	28	28	56
Ethnic Category: Total of All Subjects *	30	30	60
Racial Categories			
American Indian/Alaska Native	0	0	0
Asian	2	1	3
Native Hawaiian or Other Pacific Islander	0	0	0
Black or African American	4	4	8
White	24	25	49
Racial Categories: Total of All Subjects *	30	30	60

